16.2.3 Progression-Free Survival According to RECIST 1.1 or Modified irRC

PFS time is defined as the time from first administration of study treatment until date of the first documentation of PD or death by any cause (whichever occurs first), when death occurs within 84 days of last tumor assessment or first administration of study treatment (whichever is later).

PFS will be censored in the following scenarios:

- Subjects who do not have any post-baseline tumor assessment, or do not have a baseline tumor assessment, and die (when applicable) more than 84 days after initial avelumab dose will be right-censored on the date of first dose of study treatment.
- Subjects who have not experienced an event (PD or death) will be right-censored on the date of their last evaluable tumor assessment.
- If death without previously documented PD is observed after more than 84 days of last evaluable tumor assessment, subject will be right-censored at the date of the last evaluable tumor assessment.

$PFS = (\text{date of PD or death/censoring} - \text{date of the first dose} + 1)/30.4375$ (months).

The analysis of PFS will be performed with a Kaplan-Meier method with the same approach as for duration of response described in Section 16.2.2. Kaplan-Meier estimates (product-limit estimates) will be presented together with a summary of associated statistics including corresponding two-sided 95% CIs. In particular, the proportion of PFS at 3, 6, and 12 months will be estimated with corresponding two-sided 95% CIs. Kaplan-Meier plots of PFS time and listing of PFS will be provided as well.

Frequency (number and percentage) of patients with each event type (PD or death) and censoring reasons will be presented. Censoring reasons are as follows:

- Ongoing in the study without an event (PD or death)
- No baseline assessment
- No adequate post-baseline assessments
- No documented PD and death more than 84 days after last evaluable tumor assessment.

The PFS time or censoring time and the reasons for censoring will also be presented in a patient listing.

16.2.4 Overall Survival

OS is defined as the time from first dose to death due to any cause. For subjects who are still alive at the time of data analysis or who are lost to follow up, OS time will be censored at the date of last contact as specified in Section 18.1.

$OS = (\text{date of death/censoring} - \text{date of the first dose} + 1)/30.4375$ (months).

The analysis of OS time will be performed with a Kaplan-Meier method with the same approach as for duration of response described in Section 16.2.2. Kaplan-Meier estimates (product-limit estimates) will be presented together with a summary of associated statistics including corresponding two-sided 95% CIs. In particular, the proportion of overall survival at 6, 12, and 24 months will be estimated with corresponding two-sided 95% CIs.

The Kaplan-Meier plots of OS time and listing of OS will provided as well.

Frequency (number and percentage) of patients with an event type (death) and censoring reasons will be presented. Censoring reasons are as follows:

- Alive
- Withdrawal of consent
- Lost to follow-up

Lost to follow-up will include the following subjects:

- Lost to follow-up status is collected on the eCRF page prior to the analysis cut-off;

- Subjects with the last contact date > 14 weeks prior to the analysis cut-off date (duration of 14 weeks is based on the assessment schedule of every 12 week for survival follow-up interval + 2 week window).

The OS time or censoring time and the reasons for censoring will also be presented in a patient listing.

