7.1.4 Post-Treatment Safety Follow-Up

All subjects will have a subsequent visit scheduled 10 weeks after the last administration of avelumab. The visit will include the following full assessment of safety parameters (refer to [Appendix I](#)):

- Any treatment related AEs and concomitant medications will be documented, including further anti-cancer therapy.
- Vital signs and body weight will be measured.
- Physical examination will be performed.
- ECOG performance status will be assessed.
- 12-lead ECG will be assessed.
- Laboratory testing consisting of the following will be assessed:
 - hematology, hemostaseology, full serum chemistry, and full urinalysis
 - T4 and TSH levels
 - PK sample (any remaining sample may be used for ADA determination)
- A urine β -HCG pregnancy test (in women of child bearing potential) will be conducted.

After the End-of-Treatment visit only treatment-related AEs have to be documented until the Post-treatment Safety Follow-up visit. Subjects with a SAE ongoing at the post-treatment safety follow-up visit must be monitored and followed up by the investigator until stabilization or until the outcome is known, unless the subject is documented as “lost to follow up.”

Subjects without progressive disease according to RECIST 1.1 at the end-of-treatment visit will be followed up for radiographic disease progression (CT / MRI scans) every 12 weeks up to 1 year.

After the end-of-treatment visit, subjects will be followed quarterly (\pm 14 days) for survival (including assessment of any further tumor therapy). The survival follow-up will continue until 1 year after the last subject receives the last dose of avelumab.

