14. Endoscopic biopsies, core needle biopsies, excisional biopsies, punch biopsies and surgical specimens are suited. Fine needle aspiration biopsies are not suited. Samples can be provided as block or slides (see Section 7.6.2.4 for details). Optional tumor biopsies will be collected prior to infusion on Day 1, Day 43, and at the end-of-treatment visit (see Section 7.6.2.4 for details).

CCI

[figure not shown]
16. Adverse events will be documented at each trial visit until the End-of-Treatment visit. After the End-of-Treatment visit only treatment-related AEs have to be documented until the Post-treatment Safety Follow-up visit. Subjects with a SAE ongoing at the post-treatment safety follow-up must be monitored and followed up by the investigator until stabilization or until the outcome is known, unless the subject is documented as “lost to follow-up”. Any SAE assessed as related to IMP must be reported whenever it occurs, irrespective of the time elapsed since the last administration of IMP. Subjects without progressive disease at the end-of-treatment visit will be followed up for disease progression (CT / MRI scans every 12 weeks) up to 1 year or until disease progression, whichever is first. In addition, subjects will be followed quarterly (\pm 14 days) for survival (including assessment of any further tumor therapy). The survival follow-up will continue until 1 year after the last subject receives the last dose of avelumab. See Section 7.1.4 for details.

17. Full chemistry panel and other laboratory studies are detailed in [Table 7.2](#). Follicle-stimulation hormone at screening, if applicable (Section 7.1.1).
18. Full urinalysis at screening, the end-of-treatment, and the 10-week safety follow-up and basic urinalysis (protein content only) at each visit indicated prior to administration of study drug and at the discontinuation visit. If urinalysis (full or basic) is positive for protein, sediment will be evaluated.

Expansion Phase

Measure	Washout ^S / Screening/ Baseline Assessments	Treatment Phase													Discontinuation/ End-of- Treatment Visits	Post Treatment Safety Follow- up Visit	Post- Treatment Survival Follow-up (18)				
		Day -28 ^S / -18 to First Treatment	V1	V2	V3	V4#	V5	V6#	V7	V8#	V9	V10	V11	V12				Until Progression	Up to ≤ 7/28 Days after Last Treatment (1,2)	10 Weeks after Last Treatment	Every 3 months (18)
		W1 d1	W1 d2*	W1 d3*	W2 d8	W3 d15	W4 d22	W5 d29	W6 d36	W7 d43	W9 d57	W11 d71	W13 d85								

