	
at the post treatment safety follow-up must be monitored and followed up by the investigator until stabilization or until the outcome is known, unless the subject is documented as “lost to follow-up”.
 
Subjects without progressive disease (PD) at the end-of-treatment visit will be followed up for disease progression (CT / MRI scans every 12 weeks) up to 1 year. In addition, subjects will be followed for any AE suspected to be related to study treatment, especially for the occurrence of new autoimmune events up to 3 months after the last dose of avelumab.
 
After the end-of-treatment visit, subjects will be followed quarterly for survival (including assessment of any further tumor therapy). The survival follow-up will continue until 1 year after the last subject receives the last dose of avelumab.
 
Schedule of Assessments can be found in Section 12, Appendix I, of the protocol.

Randomization and Blinding	Not applicable.

CCI

CCI

CCI

8 Overview of Planned Analyses

This SAP will only address analyses for the expansion phase. Additional SAPs for Safety Monitoring Committee (SMC) analyses and for the final analysis of dose escalation phase have been developed separately. Trial endpoints specifically for dose escalation have been included into the dose escalation SAP.

The planned analyses for the expansion phase are summarized in Table 2. An additional interim analysis may be conducted 13 weeks after the start of treatment of the last subject in that cohort for selected primary and secondary expansion cohorts. Depending on subject enrollment or planning of future study, a separate primary analysis may be performed for selected secondary cohorts. Those analyses, as well as an interim safety analysis for interim CSR, are also included into Table 2.

Table 2 Planned Analyses for Expansion Cohorts

Cohort	Interim Analysis	Primary Analysis	Interim CSR and Final Analysis
NSCLC post platinum doublet	60 subjects 75 subjects all subjects	X	Pooled expansion cohorts for interim CSR and all expansion cohorts together for final analysis
NSCLC first-line	30 subjects 75 subjects all subjects	X	
MBC	75 subjects	X	
Gastric and GEJ cancer primary	75 subjects all subjects	X	
CRPC		X	
CRC		X	
2nd Ovarian cancer cohort	20 subjects 75 subjects all subjects	X	
ACC	20 subjects all subjects	X	
Melanoma	20 subjects all subjects	X	
Mesothelioma	20 subjects all subjects	X	
2nd Urothelial carcinoma cohort	20 subjects all subjects	X*	

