Data of subject status and survival follow-up will be provided in a listing.

18 Reporting Conventions

- Reporting will require placement of decimals, and this will depend on the raw data collected. Generally, mean and median should be displayed one more decimal place than the raw data and standard deviation should be displayed two more decimal place than the raw data. Percentages will be reported as one decimal place.
- The rounding will be performed to closest integer / first decimal using the common mid-point between the two consecutive values. E.g. 5.1 to 5.4 will be rounded to an integer of 5, and 5.5 to 5.9 will be rounded to an integer of 6.
- The following conversion factors will be used to convert days to months or years, where applicable: 1 month = 30.4375 days and 1 year = 365.25 days.
- Data listings will be sorted by dose level, subject identifier, visit or date (if applicable), or parameters, as appropriate.

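### The 14-week lost-to-follow-up limit in the OS analysis rests on a 12-week survival interval; on the documents' quarterly ±14-day schedule it is about one week too short

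*SAP*

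**What the plan says.** Expansion SAP 16.2.4 requires counts and percentages for each OS censoring reason: alive, consent withdrawn, or lost to follow-up. A subject counts as lost in either of two ways. One is a lost-to-follow-up entry on the eCRF before the cut-off. The other is a date rule: "Subjects with the last contact date > 14 weeks prior to the analysis cut-off date". The SAP explains the limit in brackets: "duration of 14 weeks is based on the assessment schedule of every 12 week for survival follow-up interval + 2 week window".

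The survival schedule is given in three other places:

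- Protocol 7.1.4: "subjects will be followed quarterly", with a window of 14 days either side.
- Protocol Appendix I, expansion schedule: the survival follow-up column is every 3 months, and its footnote repeats quarterly ±14 days.
- Expansion SAP section 6, schedule of visits: "subjects will be followed quarterly for survival (including assessment of any further tumor therapy".

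In post-treatment follow-up, the protocol and the SAP summary use 12 weeks for CT/MRI scans in subjects without progression, for up to one year.

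**The concern.** The limit appears to borrow the scan interval for the survival contacts. A limit built on too short an interval expires before the permitted contact window closes. If the cut-off falls between the two dates, a subject whose next contact is not yet overdue is reported as lost.

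Nothing else in the SAP corrects this. Section 18.1 does not let assessment dates after the cut-off count towards last contact, so a contact made a few days later, still within the window, cannot rescue the classification. Subjects recorded as lost on the eCRF are already caught by the other criterion, so the date rule only adds subjects not so recorded. The disposition table in 12.1 takes its reasons from the eCRF, so the same subject could be in follow-up there and lost in the OS table.

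What is at stake is a reported count. Readers of single-arm survival data commonly look at the alive/lost split to judge how complete follow-up is, although the documents do not themselves assign it that use.

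**Working it through.** **Inputs**

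- Limit: more than 14 weeks; basis 12 weeks + 2 weeks (expansion SAP 16.2.4).
- Survival interval: quarterly / 3 months; window ±14 days (protocol 7.1.4 and Appendix I).
- Conversion: "1 month = 30.4375 days and 1 year = 365.25 days" (expansion SAP 18, Reporting Conventions).
- Assumed, because the documents do not give it: when contacts fall within the window, and whether the 3-month clock restarts at each contact (rolling) or runs from fixed due dates (anchored).

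**The SAP's own figure**

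12 + 2 = 14 weeks; 14 × 7 = 98 days. It reproduces.

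**The same formula with the documented interval**

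- 3 × 30.4375 = 91.3 days (13.04 weeks).
- Interval + window: 91.3 + 14 = 105.3 days (15.04 weeks).
- Shortfall of the SAP limit: 105.3 − 98 = 7.3 days.
- By calendar, a 3-month span between 2013 and 2019 is 89 to 92 days, so interval + window is 103 to 106 days.

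**Who is affected**

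- Contact on every nominal date: the gap is at most 92 days, below 98. Never flagged.
- Rolling schedule, next contact late in the window: flagged from day 99 to about day 105.
- Anchored schedule, one contact 14 days early and the next 14 days late: the gap reaches 91.3 + 28 = 119.3 days (17.04 weeks), or 92 + 28 = 120 days by calendar.

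**Share mislabelled at a random cut-off**

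This is E[max(gap − 98, 0)] / E[gap], for compliant subjects and counting survival contacts only.

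- Rolling, contact uniform within ±14 days: the gap is uniform on 77.3 to 105.3 days. The mean excess is 7.3125² / (2 × 28) = 0.955 days; 0.955 / 91.3 = **1.0%**.
- Anchored, each contact uniform within ±14 days: the deviation of the gap from 91.3 days is triangular on ±28 days, and 98 − 91.3125 = 6.6875. The mean excess is (28 − 6.6875)³ / (6 × 28²) = 2.058 days; 2.058 / 91.3 = **2.3%**.
- Rolling, every contact 14 days late: 7.3125 / 105.3125 = **6.9%**.

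**The case against.** The best reply is that this is a small labelling matter. The sum 12 + 2 = 14 is correct; the fault is an inconsistency between passages. OS times do not move, because subjects classed as alive and as lost are both censored at last contact, so Kaplan-Meier estimates and confidence intervals are the same either way. OS is a secondary endpoint analysed descriptively. The disposition table gives a separate count from the eCRF, and the OS listing shows each subject's censoring time and reason. A limit that is too short overstates loss, which does not flatter the trial. All of this stands.

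The percentages are also open to challenge, and fairly so. Section 18.1 takes the latest of many dates, including laboratory draws, ECGs, scans, adverse events and later anti-cancer therapy. Subjects on treatment are seen every 2 weeks and are untouched. Those without progression have scans for up to a year. The figures therefore apply to subjects whose only remaining contacts are the survival calls, and are lower elsewhere.

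A reader might infer that subjects followed exactly to schedule are reported as lost. The documents do not support that: a contact on each nominal date leaves at most 92 days. A reader might also infer that the limit must be 17 weeks. That holds only on an anchored schedule, which the protocol does not specify. The 6.9% case, by contrast, needs a rolling schedule; on an anchored one, a subject always 14 days late has gaps of 91.3 days and is never flagged. The two extremes cannot be combined.

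The reply does not remove the core: the stated 12-week basis conflicts with the protocol and with the SAP's own summary, and the limit derived from it expires before the permitted window closes.

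**Conclusion.** The point holds as a minor inconsistency with a definite effect on one reported count. On the documents' survival schedule, the SAP's interval-plus-window rule gives 105.3 days, so the 98-day limit is about 7 days short. Living subjects contacted late but within the window can be reported as lost.

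The likely size is about 1.0% to 6.9% of subjects in survival follow-up at a random cut-off. It depends on the assumed contact timing and on survival contacts being the only source of last-contact dates. The exposure is greatest at the final analysis, with its cut-off 1 year after the last dose in the expansion phase, when no one is on treatment. Only the alive/lost split in the OS censoring table and listing is affected; there is no ground for inferring a bias in the survival estimates.

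**What to change.** In expansion SAP 16.2.4, replace the bracketed basis with quarterly follow-up ±14 days, and replace the 14-week limit with 3 months + 14 days: more than 105 days by the SAP's conversion, or more than 106 days to cover every calendar quarter. If survival contacts are in fact anchored to fixed dates, say so and use about 17 weeks; 120 days covers every calendar quarter, since 17 weeks is 119 days. If 12 weeks was intended, give the reason.

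The cost is one number and one phrase. The downside is that a subject who is truly lost, but not recorded as such on the eCRF, is recognised about 1 week later, or about 3 weeks later with the anchored limit.

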16.2.5 Time to Response per RECIST v1.1 or Modified irRC

TTR will be analyzed for subjects with confirmed CR/PR based on investigator and/or IERC assessments and subjects with irCR/irPR based on investigator assessment.

$$\text{TTR (in weeks)} = (\text{first date of objective response} - \text{first dose date} + 1) / 7$$

TTR will be summarized using simple descriptive statistics (mean, SD, median, min, max, Q1, Q3).

16.2.6 Subgroup Analyses

Subgroup analyses will be performed according to the following parameters:

- PD-L1 expression status based on:
 - Tumor cell (positive, negative)
 - Positive: $\geq 1\%$ of the tumor cells show PD-L1 membrane staining intensity $\geq 1+$. Negative: $< 1\%$ of the tumor cells show PD-L1 membrane staining intensity $\geq 1+$. Evaluable: positive + negative.
 - Positive: $\geq 5\%$ of the tumor cells show PD-L1 membrane staining intensity $\geq 1+$. Negative: $< 5\%$ of the tumor cells show PD-L1 membrane staining intensity $\geq 1+$. Evaluable: positive + negative.
 - Positive: $\geq 25\%$ of the tumor cells show PD-L1 membrane staining intensity $\geq 2+$. Negative 1: $< 5\%$ of the tumor cells show PD-L1 membrane staining intensity $\geq 1+$. Negative 2: $\geq 5\%$ of the tumor cells show PD-L1 membrane staining intensity $\geq 1+$ but $< 25\%$ of the tumor cells show PD-L1 membrane staining intensity $\geq 2+$. Negative: negative 1 + negative 2. Evaluable: positive + negative.
 - Positive: $\geq 50\%$ of the tumor cells show PD-L1 membrane staining intensity $\geq 1+$. Negative: $< 50\%$ of the tumor cells show PD-L1 membrane staining intensity $\geq 1+$. Evaluable: positive + negative.
 - Positive: $\geq 80\%$ of the tumor cells show PD-L1 membrane staining intensity $\geq 1+$. Negative: $< 80\%$ of the tumor cells show PD-L1 membrane staining intensity $\geq 1+$. Evaluable: positive + negative.

Immune cell (positive, negative, evaluable (positive + negative)). Subjects will be considered PD-L1 positive if tumor has hotspots with at least 10% PD-L1 expressing immune cells (see also Section 13.4).

- Demographics
 - Age (<65, ≥65 years)
 - Sex (male, female)
 - Race (white, others)
 - ECOG (0, ≥1)
- Pooled Geographical region
 - North America
 - Europe
 - Asia
- Region (Asia, Non-Asia) for gastric and GEJ cohorts
- Smoking status: never smoked, ever smoked (containing regular user, occasional user, and former user).
- Histology (adenocarcinoma, squamous cell carcinoma, others). This only applies to NSCLC cohorts.
- Tumor sub-site (oral cavity, oropharynx and hypopharynx, larynx). This only applies to HNSCC cohorts.
- Tumor size at baseline: sum of target lesion diameters \geq vs $<$ median
- Presence of metastases at baseline (present, absent). Target or non-target lesions that are categorized as ‘metastasis’ are classified as metastases.
- Prior anti-cancer drug therapy
 - # of any prior anti-cancer therapy lines (≤ 1 , 2, ≥ 3).
 - # of prior anti-cancer therapy lines for metastatic or locally advanced disease (≤ 1 , 2, ≥ 3).
 - # of any prior anti-cancer therapy lines (≤ 1 , >1 : for NSCLC post platinum doublet).
 - # of prior anti-cancer therapy lines for metastatic or locally advanced disease (≤ 1 , >1 : for NSCLC post platinum doublet).
- NSCLC biomarker
 - EGFR (normal, abnormal, unknown)
 - KRAS (normal, abnormal, unknown)
 - ALK (normal, abnormal, unknown)
 - EGFR/ALK (normal, abnormal, unknown)
- MBC biomarker: HER2- (ER- and PR-), HER2- (ER+ or PR+), HER2+, or unknown

- Gastric and GEJ cancer biomarker: HER2+, HER2-, or unknown
- HNSCC biomarker: HPV+, HPV-, or unknown
- Gastric and GEJ cancer and ovarian cancer biomarker: MSI (low vs. stable vs. high)
- Gastric and GEJ cancer biomarker: EBV (positive vs. negative)
- MBC and ovarian cancer biomarker: BRCA1/2, mutant (if at least one mutation in both genes) vs. wildtype (no mutation in BRCA1 and BRCA2)
- Gastric and GEJ cancer biomarker: PD-L1 expression status according to each of the three alternative scoring methods (conventional tumor cell (TC) scoring, immune cell (IC) scoring, aggregated (TC + IC) scoring): PD-L1 assay status at cut-off value as follows:
 - < 1% vs. ≥1%
 - < 5% vs. ≥5%
 - < 25% vs. ≥25%
- Eligibility for platinum-based therapy (yes, no) for urothelial carcinoma cohort
- Baseline laboratory assessment (only presented for urothelial carcinoma efficacy and secondary cohorts)
 - Albumin (< 35 g/L vs. ≥ 35 g/L)
 - Hemoglobin (< 100 g/L vs. ≥ 100 g/L)
- Baseline Bellmunt Scores (only presented for urothelial carcinoma efficacy and secondary cohorts)
- Time since last prior anti-cancer chemotherapy (only presented for urothelial carcinoma efficacy and secondary cohorts)
- Sub-site of tumor (only presented for urothelial carcinoma efficacy and secondary cohorts)
 - Upper tract defined as ureter or renal pelvis
 - Lower tract defined as bladder or urethral

Frequency of objective response, percentage, and 95% CI of ORR will be estimated for all the subgroup analyses on BOR or irBOR. CI will be based on exact Clopper-Pearson method. For subgroup analyses of BOR or irBOR based on PD-L1 expression status, the p-value and 80% CI will be provided as well. The p-value will be based on Fisher's exact test for association between PD-L1 status (positive vs. negative) and ORR.

Same statistics will be provided for the subgroup analyses on PFS, irPFS, and OS as those provided for non-subgroup analyses on PFS, irPFS, and OS, respectively. For subgroup analysis by PD-L1 status, the hazard ratios and their associated 95% CIs will be estimated by Cox Proportional Hazards model using PD-L1 status (negative as reference) as covariate.

The subgroup analyses are exploratory for all the cohorts and will be primarily performed on IERC data for efficacy expansion cohorts and the urothelial carcinoma secondary cohort. Subgroup

analysis will not be performed if the largest subgroup covers $\geq 90\%$ of the subjects. Subgroup analysis to be performed depends on the cohorts and type of analysis, but in general:

- Subgroup analysis by PD-L1 status applies to interim and primary analyses for all the expansion cohorts if PD-L1 data is available.
- Subgroup analyses by demographic and prior anti-cancer therapy line apply to all the expansion cohorts. Subgroup analysis by sex is excluded for MBC, CRPC, and ovarian cancer cohorts.
- Subgroup analysis by geographic region applies to all the cohorts with subjects enrolled from different regions.
- Subgroup analysis of tumor response (confirmed/unconfirmed BOR, irBOR) by baseline tumor size applies to all expansion cohorts.
- Subgroup analysis of tumor response (confirmed/unconfirmed BOR, irBOR) and PFS by the status of metastases at baseline applies to urothelial carcinoma cohorts only.
- Subgroup analysis by biomarker applies to interim and primary analyses for NSCLC, MBC, gastric and GEJ cancer, HNSCC cohorts based on the above definitions.
- Subgroup analysis by histology or tumor sub-site applies to NSCLC or HNSCC cohorts, respectively.
- Subgroup analysis by smoking status applies to NSCLC and HNSCC cohorts.
- Subgroup analyses by eligibility of platinum-based therapy and baseline albumin and hemoglobin apply to urothelial carcinoma cohorts only.

Subgroup analyses may be also performed on selected sub-population such as PD-L1+ subjects based on tertiary cut-off defined in [Section 13.4](#). The details will be provided in the Table, Listing, and Figure Shells document.

The association between unconfirmed/confirmed objective response and PD-L1 status (based on tertiary cut-off) will be stratified by PD-L1 sampling time related to the first date of prior anti-cancer therapy for metastatic or locally advanced disease (before, after) and summarized in a table. This will apply to post-platinum doublet NSCLC cohort.

[figure not shown]
The maximum target lesion percentage reduction vs. percentage of tumor cells with any staining ($\geq 1+$) or with $\geq 2+$ staining will be displayed graphically using scatterplot.

Subgroup information and BOR, PFS, or OS will be presented in three separate data listings.

